Monday, April 23, 2018

BRIEF ADMISSION SKÅNE: REPLACING GENERAL ADMISSION FOR INDIVIDUALS WITH SELF-HARM AND ACUTE RISK OF SUICIDE.

The Brief Admission Skåne Randomized Controlled Trial (BASRCT)

Aims:

The overall aim of this study is to determine whether Brief Admission Skåne (BA) can replace General Admission (GA) to hospital, for individuals that self-harm at risk for suicide.

Primary Research Question:

1. Can BA replace GA for individuals with self-harm at acute risk for suicide?

Secondary Research Questions:

2. Can BA increase the individual's level of functioning in activities of daily life?
3. Can BA increase the individual's ability to cope effectively with life stress?
4. Can BA reduce the individual's global psychiatric symptoms?
5. Can BA reduce the frequency of all self-harming behaviours including suicide attempts?
6. Can BA reduce the severity of self-harming behaviours?
7. Can BA serve as feasible management model in the care of individuals with self-harm, who may also be at risk for suicide?
8. Can the *Five Self-Harm Behaviour Groupings Measure* reliably and validly measure behaviours ranging from indirect to direct self-harm and attempted suicide, with varying degree of frequency and severity?

Area overview:

A recent study examining the prevalence of self-harm in psychiatric settings in Sweden, found that almost half of the individuals currently receiving mental-health services had self-harmed during the past six months (Odelius & Ramklint, 2014). Of those who had engaged in self-harming behaviour, more than 90% have had suicidal thoughts during their life-time and more than every other had at least once during their lives attempted suicide. For a small group of individuals, acts of self-harm are frequent and risk for suicide is recurrent, prolonged and high (Lieb, Zanarini, Schmahl, Linehan & Bohus, 2004). Many of these individuals are diagnosed with Borderline Personality Disorder (BPD).

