Brief Admission (BA – Brukarstyrd inläggning) is in this project defined as the specific intervention, standardized by the Brief Admission Skåne Fidelity Measure (BASF, Bilaga 2b; Liljedahl, Helleman, Daukantaite & Westling, 2017). *Brief Admission Skåne (BAS - Brukarstyrd inläggning Skåne)* is the randomized controlled trial evaluating the intervention.

General Admission (GA – Läkarstyrd inläggning) is defined as all other admissions, voluntary as well as coercive, to the emergency ward (psychiatric or somatic) due to psychiatric needs or following an act of self-harm or a suicide attempt, including possible following days with hospital admission.

Patient selection criteria

Inclusion criteria:

- Current episodes of self-harm and/or recurrent suicidality.

- Fulfilling at least three criteria for Borderline Personality Disorder.
- Admitted to hospital care for at least 7 days or presenting to the psychiatric emergency department at least 3 times during the last six months.
- Age 18-60 years.

Exclusion criteria:

- No current ambulatory clinician
- No current place to live (homeless).
- Medical disorder from other organs that significantly contributes to symptoms (e.g. if self-harm only occurs during episodes of hypoglycemia in a diabetic patient).

Testing for autism, attention deficit or learning disabilities exceed the scope of this study. These diagnoses are not considered to be exclusion criteria, neither are they related in a more direct way to any of the research objectives. Thus, since the proposed assessments already are considerably time-consuming (see justification for measures, below), testing for these diagnoses is excluded.

Methods of evaluation (Figure 1, Bilaga 2c and Bilaga 5a-j)

Data collected from hospital records

From local hospital records, data is collected concerning:

- Number of days with general admission to hospital
- Visits at the psychiatric emergency department,
- Whether the admission was voluntary or coercive
- Coercive acts as defined by LPT; 1991:1128: §19, 20, 21, 22, 23 and 24.

Hospital data are collected monthly retrospectively from twelve months before the intervention start of the pilot and until endpoint after 12 months of the active study period. This generates quantitative data registered in a form (Bilaga 5a).

Justification for Measures

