A defining feature of the BA is that the participant decides for themselves regarding whether and when to initiate a brief hospital admission, at most three times per month, and for a maximum of three consecutive days. BAs can be initiated between 8AM and 8PM every day during the week. The procedure for the BA is defined in the BASP. If the needs of the client exceed the level of service offered during BA, GA should be considered.

The intervention will last for 12 months and the participant will evaluate the intervention at the end of each BA and the contract after 6 and 12 months according to the procedure as described in BASFM (Bilaga 2b; Liljedahl, Helleman, Daukantaite & Westling, 2017). Participants randomized to the BA condition have access to the same security procedures as they do when receiving Treatment as Usual (TAU).

No risks to the well-being of the participant are expected, exceeding those found with TAU. Normal security routines are therefore sufficient. Data collection will start in September 2015 for the pilot phase of the study, and evaluated at the end of January 2015.

How is the choice of methods related to the Research Objectives?

1. Can BA replace GA for individuals with self-harm and acute risk for suicide?
 - Outcome is data from medical records.
2. Can BA increase the individual's level of functioning in activities of daily life?
 - Outcome is data from WHODAS 2.0. (World Health Organization, 2014).
3. Can BA increase the individual's ability to cope effectively with life stress?
 - Outcome is data from Brief COPE (Carver, 1997) Swedish version of the Brief COPE (Muhonen & Torkelson, 2005) and DERS (Gratz & Roemer, 2004); Swedish version of the DERS (Friberg, 2006).
4. Can BA reduce the individual's global psychiatric symptoms?
 - Outcome is data from estimation according to CGI-S (Guy, 1976).
5. Can BA reduce the frequency of all self-harming behaviours including suicide attempts?

- Outcome is data from questionnaire 5S-HM (Liljedahl & Westling, 2014) and ISAS (Klonsky & Glenn, 2009; Glenn & Klonsky, 2011; Lindholm, Bjärehed & Lundh, 2011).

6. Can BA affect the severity of self-harming behaviours including suicide attempts?
 - Outcome is data from questionnaire 5S-HM (Liljedahl & Westling, 2014).
7. Can BA serve as a feasible management option in the care of individuals with self-harm who may also be at risk for suicide?

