 - Outcome is data from IES and the CES (Liljedahl, Helleman, Daukantaite & Westling, 2017) completed by the participants and clinicians administering BA after pilot testing, 6 and 12 months
8. Can the *Five Self-Harm Behaviour Groupings Measure* (5S-HM: Liljedahl & Westling, 2014) reliably and validly measure behaviors ranging from indirect to direct self-harm and attempted suicide, with varying degree of frequency and severity?
 - Outcome is data from questionnaire 5S-HM (Liljedahl & Westling, 2014), ISAS (Klonsky & Glenn, 2009; Glenn & Klonsky, 2011); Swedish version of the ISAS (Lindholm, Bjärehed & Lundh, 2011) and DERS (Gratz & Roemer, 2004); Swedish version of the DERS (Friberg, 2006).

Required sample size and a priori power analyses

G*Power, 3. 1. 7 (Faul, Erdfelder, Lang, & Buchner, 2007) was used to calculate a priori power for analyzing main effects and interaction for an A X B mixed design where A is a between-subject factor with two levels (experimental and control groups) and B is a within-subjects factor with three levels (three repeated assessments). The main statistical analyses will be either mixed (within-between) Analysis of Variance (ANOVA) or Analysis of Covariance (ANCOVA), controlling for baseline. Simpler univariate analyses will be calculated, but the power analyses summarized here are for the ANOVA model.

Assuming that three effects (i.e., between levels of the factor A, within levels of the factor B and within-between interaction A X B), are of medium size ($f = 0.25$; see Cohen, 1988), a significance level is of $\alpha = .05$, and the power values of the F tests are .85, a total of $N = 98$ per treatment site must be recruited ($n=196$ including both Stockholm and Lund, whose data will be grouped and analyzed separately).

Attrition in this population based on previous studies has been estimated to be approximately 25% (Stoffers, Völlm, Rucker, Timmer, Huband & Lieb, 2012; Nadort, Arntz, Smit, Giesen-Bloo, Eikelenboom, Spirnhoven, van Asselt, Wensing, & van Dyck., 2009). In order to attain the required sample size for these power estimates, including expected attrition, a total of $N= 124$ participants is required, with $n=62$ participants in each group (treatment and control).

Significance:

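### The primary question is tied to a data source, not to one measure, effect and model, so a 5% false-positive rate for the primary conclusion is not assured

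*Combined protocol and SAP*

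**What the plan says.** The primary research question under Aims is "Can BA replace GA for individuals with self-harm at acute risk for suicide". The section relating methods to research objectives gives its outcome, in item 1, as "Outcome is data from medical records". It names no variable, time window, summary or test. Items 2 to 8 in the same section each name specific instruments.

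The section on data collected from hospital records lists four items:

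- GA days, given as "Number of days with general admission to hospital"
- psychiatric emergency visits
- the status of each admission, voluntary or coercive
- coercive acts under six sections of the compulsory care law (LPT)

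None is called primary. GA days is singled out once, in the Study design section, as the series to be monitored monthly in the time-series subset.

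The section on required sample size used G*Power to "calculate a priori power for analyzing main effects and interaction for an A X B mixed design", with two groups, three assessments, alpha .05 and power .85. It leaves the main analysis as mixed ANOVA or baseline-controlled ANCOVA and says simpler univariate analyses will also be run. No section gives a hierarchy, a co-primary rule, a division of alpha or any other multiplicity adjustment.

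**The concern.** A 5% significance level describes the primary conclusion only if one test, fixed in advance, decides it. Here three choices are open: which record measure, which treatment-related effect (group or group-by-time), and which model. Each can be settled after the data are seen without departing from the plan.

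At stake is a claim that one form of hospital admission can replace another in people who self-harm and are at risk of suicide. A reader of the final report could not tell from the protocol whether the result carrying that claim was the one intended from the start.

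**Working it through.** **Inputs from the documents.** Two groups, three assessments (m = 3), f = 0.25, alpha .05, power .85 and N = 98 before attrition (required sample size section); four record items (hospital records section).

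**Assumed, because not given.** Correlation 0.5 between repeated assessments; correlation r between record measures varied from 0 to 0.9; normally distributed outcomes in the simulations. The any-significant-result rule is also an assumption, used only to size the exposure.

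**1. The plan's own figure.** For the between-group effect, lambda = N × f² × m / (1 + (m − 1) × rho), with 1 and N − 2 degrees of freedom. At N = 98 and rho = 0.5, lambda = 98 × 0.0625 × 3 / 2 = 9.19 and power is 85.1%, so 98 reproduces. At rho = 0, 0.3 and 0.7 this effect would need 50, 80 and 118. The interaction, with lambda = N × f² × m / (1 − rho), needs only 32 at rho = 0.5. The stated size therefore fits one between-group F test at the full .05.

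**2. GA days alone, group and interaction tests.** 1 − 0.95² = 9.75%. Simulated null mixed ANOVAs (N = 98, 20,000 repetitions) give 10.1%.

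**3. One test on each measure, if independent.** Four measures: 1 − 0.95⁴ = 18.5%. Three measures, if voluntary or coercive status only describes an admission: 1 − 0.95³ = 14.3%.

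**4. Two tests on each of four measures, if independent.** 1 − 0.95⁸ = 33.7%.

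**5. Correlated measures.** Chance of at least one two-sided rejection on four measures, from simulated null mixed ANOVAs (N = 98, 10,000 repetitions per row, so simulation error is about half a percentage point or less):

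| r between measures | Group test only | Group and interaction |
|---|---|---|
| 0 | 17.7% | 33.1% |
| 0.3 | 16.8% | 32.3% |
| 0.5 | 15.8% | 29.4% |
| 0.7 | 13.5% | 25.2% |
| 0.9 | 9.0% | 18.1% |

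**6. Direction.** These are two-sided rates and include chance results favouring TAU. For four group tests, the chance of at least one false result favouring BA is 1 − 0.975⁴ = 9.6% if independent, and by simulation 7.8% at r = 0.5 and 6.5% at r = 0.7. The comparator for a single two-sided test is 2.5%.

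**7. If all tests were kept and adjusted instead.** Bonferroni over four tests (.0125) lowers between-group power at N = 98 to 68.6% and would need N = 138 before attrition. Over eight tests (.00625) the figures are 59.4% and N = 156.

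**The case against.** A reader might infer that the plan adopts a rule under which any significant record measure answers the primary question, and hence that its true error rate is several times a promised 5%. The documents support neither step. No section says that one positive result would suffice. Alpha .05 appears as an input to the power calculation for the F tests; it is not promised for the primary conclusion as a whole.

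Four endpoints may also be an overcount. The list describes data to be collected, not hypotheses to be tested. The Definitions section counts voluntary and coercive admissions alike as GA, so that status may be only an attribute of an admission, and emergency visits may overlap with GA. The question is about GA, days of GA is the first item listed, and the time-series component uses it, so GA days is the evident candidate. Nor does the plan say that both the group and the interaction effect count as evidence on this question.

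All of this stands, and it limits the point to what is not assured. It does not remove it. With GA days accepted as the intended measure, two unadjusted treatment tests still give about 10% if either may carry the claim, before the open ANOVA or ANCOVA choice and the univariate analyses are counted. An evident candidate is also not a commitment.

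**Conclusion.** The point holds in a limited form: the plan does not fix the measure, effect or model for the primary question, so it does not secure 5% for the primary conclusion. This is more than missing wording, because the choices left open affect the error rate and can be made after seeing the results.

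The calculated error rates are conditional. They describe what would follow if any significant treatment test were taken as the answer, and they depend on between-measure correlations that the documents do not give. They bound the exposure and do not measure an error rate that the plan has adopted. The lowest two-sided figure among the scenarios examined, four group tests at r = 0.9, is 9.0%.

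**What to change.** Name one primary variable and one test: GA days over the 12-month follow-up, BA+TAU versus TAU, in one stated model adjusted for baseline GA days and the site stratum, two-sided .05. Fix this before the data are analysed. Make emergency visits, coercive admissions, coercive acts, the group-by-time effect and any alternative models or univariate analyses secondary.

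The text change is short, and no division of alpha is needed, so the sample size need not rise on that account. The scientific cost is that the other record measures can no longer carry the primary claim. The protocol is dated April 2018 and active data collection was planned from March 2016, so the change should be a dated amendment stating that outcomes by arm had not been examined.

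The Testing Schedule sets the baseline date at randomization for controls and at the contract for the intervention group. That is a separate issue, and this change does not resolve it.

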The self-report and clinician-administered assessments in this section were included after careful and repeated consultation within the research group, balancing sensitivity to the needs of the individuals with the aim to answer the research questions at the core of this study. The shortest and most concise versions of the measures were selected, and the frequency of assessment intervals (see the Design section below) was specifically chosen to reduce the burden to the individual when completing the measures of the study.

Included in the protocol are three different self-harm measures, two of which are self-report, and one that is clinician-administered. Although the same behaviour (self-harm) is ultimately being queried, both self-report self-harm measures evaluate different, non-overlapping aspects of the behaviour. The clinician-administered self-harm measure is being validated in this study for use in clinical samples (Liljedahl & Westling, 2014). It is based upon a broad definition of self-harm that involves querying self-harm that is direct, indirect, lower-to-higher severity and lower-to-higher lethality, including suicide attempts. If this measure does prove to be reliable and valid, then future researchers and clinicians can use it rather than self-report measures based on narrow self-harm definitions that do not reflect the nature of severe and repetitive self-harm that can and does escalate into suicidal behaviour for some individuals.

Two additional steps included in this protocol to respond to the sensitivity of individuals in distress, are:

1. To ensure that individuals are not left on their own while completing self-report measures. They will be in the presence of an experienced research nurse who can support and encourage them to take breaks or discuss any items with which they might struggle.
2. To pilot the evaluation measures and the new self-harm measure (5S-HM) with individuals that have lived experience of self-harm, as well as the significant others in their lives through the Swedish voluntary organization SHEDO (self-harm and eating disorders organization: www.shedo.org). Candidates from SHEDO have already agreed to participate in the piloting of these new measures. Their feedback will be integrated to the phrasing of the new measures as well as the manner in which they are administered.

Self-report measures/ evaluations

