 - b. For individuals randomized to the intervention group data from hospital records and CGI-S (Guy, 1976), are recorded with baseline date on the day for the contract (i.e. day when BA is accessible).
8. Data collection at baseline by a Research Assistant (RA):
 - a. After randomization PI contacts a local RA who schedules an appointment with all participants, and administers a link to the self-administered forms:
 - i. 5S-HM (Liljedahl & Westling, 2014),
 - ii. WHODAS 2.0 (WHODAS 2.0; 2014),
 - iii. Brief COPE (Carver, 1997; Muñoz & Torkelson, 2005), DERS (Gratz & Roemer, 2004; Friberg, 2006),
 - iv. ISAS (Klonsky & Glenn, 2009; Glenn & Klonsky, 2011; Lindholm, Bjärehed & Lundh, 2011).
 - b. RA is available for the individual and provides help if necessary, when completing the forms online.
 - c. For individuals randomized to the intervention group RA further contacts their primary clinician as well as ward staff at the ward providing BA, to schedule an appointment for negotiation resulting in a BA contract. At the end of the negotiation IES and CES (negotiation part) are completed online.
9. Data collection at 6 and 12 months (± 2 weeks) is repeated as baseline, with the change that the contract negotiation is replaced by contract evaluation for the intervention group and data from hospital records is collected from the previous 6 months.

Pilot phase

The first three months of the study (Sept, 2015 – Jan, 2016) will form a pilot phase with the goal of optimizing the intervention, evaluate the inclusion and exclusion criteria and preliminary testing to determine whether the quality and quantity of assessments are adequate and feasible. At the termination of the pilot phase evaluation with IES and CES (Liljedahl, Helleman, Daukantaite & Westling, 2017) will be performed.

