Although individuals diagnosed with Borderline Personality Disorder (BPD), with recurrent risk for self-harm and suicide, frequently seek help in psychiatric care, there is no consensus regarding how to they are best treated when in crisis with high risk for suicide. As is the nature of individuals diagnosed with BPD or those with pervasive emotion dysregulation, suicidality has been described as “chronic” (Linehan, 1993). Accordingly, an evidence-based model of managing suicidal crises will be a significant contribution to the care of these individuals and their care-providing network.

The variation in the care offered to these individuals is, at the moment, vast. These individuals are critically ill with mortality from suicide of approximately 10%, which is 50 times higher than in non-clinical populations (Lieb, Zanarini, Schmahl, Linehan & Bohus, 2004). Brief Admission(BA) has the potential to serve as a new strategy, offering brief and structured hospital admission with low risk of iatrogenic reinforcement of suicidal behaviour. A protocol for managing crises may reduce the stress that professionals responsible for therapeutic outcomes often experience, which has often unfortunately led to stigma of these individuals within the health and mental health care system (NICE, 2004). Reduced stress amongst attending mental health professionals may in turn result in better care, as well as a larger number of clinicians becoming willing to work with individuals with recurrent and prolonged risk for suicide and self-harm or a BPD diagnosis.

Preliminary results

None.

Previous experience:

[name] is a nurse and post-doctoral researcher from the Netherlands with extensive experience in working with BA. In the Netherlands BA is a well-established treatment intervention, with a history of 30 years. Among the other researchers are senior psychiatrists ([name] and [name]) who both have experience in treating individuals with BPD at risk for self-harm and suicide. [name] has a doctorate in clinical psychology based on a scientist-practitioner model, and has extensive clinical and research experience in the field. The few existing publications have not identified any risks or complications related to the intervention.

Relevant security measures

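### Question 5 (self-harm including suicide attempts) rests only on questionnaires that stop when a participant leaves or dies, with no method for missing forms and no record-based count of attempts or deaths

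*Combined protocol and SAP*

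**What the plan says.** Under the heading that links methods to research objectives, item 5 asks "Can BA reduce the frequency of all self-harming behaviours including suicide attempts" and gives its source as "Outcome is data from questionnaire 5S-HM (Liljedahl & Westling, 2014) and ISAS". No other source is named.

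The Testing Schedule (item 8) says how the forms are obtained: a research assistant "schedules an appointment with all participants, and administers a link to the self-administered forms", and 5S-HM and ISAS are both on that list. Item 9 adds that "Data collection at 6 and 12 months (± 2 weeks) is repeated as baseline". The section on hospital records describes monthly retrospective extraction up to the 12-month endpoint. It lists General Admission (GA) days, psychiatric emergency visits, voluntary or coercive status, and coercive acts. Self-harm events, suicide attempts and deaths are not listed.

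The sample size section states: "Attrition in this population based on previous studies has been estimated to be approximately 25" per cent. Study design promises an intention-to-treat analysis in which the data of participants who drop out are kept in every analysis. The named analyses are mixed ANOVA or baseline-adjusted ANCOVA. Neither section says what happens to forms never completed or to forms due after a death.

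**The concern.** Both questionnaires need a living participant who is still taking part. Those whose self-harm escalates may be among the most likely to leave, and Question 5 then loses the later course of the people it most needs to describe. If that loss also differs by arm, the comparison is biased.

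Unequal loss is possible by design. According to the section on the intervention and TAU, the research assistant is also the nurse clinician and contact person for Brief Admission (BA) participants, and TAU participants have no such contact. The documents do not show in which direction, or how far, this would move retention.

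The records could be read for every randomised participant without a visit, yet no research question uses them for attempts or deaths. For a trial asking whether BA can replace GA in people at acute suicide risk, the report would have no count of hospital-treated attempts or deaths covering everyone randomised.

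**Working it through.** **1. The plan's own figure.** Inputs from the sample size section: f = 0.25, α = 0.05, power 0.85, two groups, three assessments. The correlation between assessments is not given; I assume ρ = 0.5. For the between-group effect, λ = f²·N·m / (1 + (m − 1)ρ) = 0.0625 × 98 × 3 / 2 = 9.19, on 1 and 96 degrees of freedom. Power is 0.851, and 98 is the smallest even total that reaches 0.85. The stated 124 follows from 98 × 1.25 = 122.5, rounded up to an even total. (Dividing by 0.75 gives 131; that is a separate matter.)

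With 25% attrition from 124, 124 × 0.25 = 31 lack final forms and 93 remain. Power is then 0.832 against 0.85 planned. The loss of precision is small, so the issue is bias.

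**2. The sources side by side.**

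| | Question 5 | Question 1 (GA) |
|---|---|---|
| Source | 5S-HM, ISAS | medical records |
| Needs the participant | yes | no |
| After leaving | no forms | records can still be read, consent permitting |
| After death | no forms | no further GA days; death not a listed item |

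**3. What 25% missing leaves open.** Take a yes/no outcome (any attempt in 12 months) with 25% missing in each arm (equal loss assumed). Each arm's rate is 0.75 × observed + 0.25 × missing, and the missing rate can lie anywhere from 0 to 1. Each rate is therefore open over 25 points, and the risk difference is 0.75 × the completers' difference ± 25 points. These are extreme bounds, not expected values.

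**4. How a false difference could arise.** All rates here are assumed except the 25% average attrition. Let the true risk be 27.5% in both arms and 50% among dropouts. Completers then show (0.275 − a × 0.50) / (1 − a), where a is attrition:
- a = 0.15: 0.200 / 0.85 = 23.5%
- a = 0.35: 0.100 / 0.65 = 15.4%
- a = 0.25: 0.150 / 0.75 = 20.0%

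With 15% loss under BA and 35% under TAU, completers show a false 8-point difference against BA (23.5 − 15.4 = 8.1). Swapping the losses reverses the sign. With 25% in both arms there is no false difference, but both arms read 20% instead of 27.5%.

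**5. On a score.** Suppose completers show d = 0.5 (f = 0.25). The effect in all randomised is 0.75 × 0.5 + 0.25 × d among the missing: 0.375 if that is 0, and zero if it is −1.5.

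**6. Deaths.** At assumed 12-month suicide risks of 0.5%, 1% and 2%, the expected deaths among 124 are 0.6, 1.2 and 2.5. One death at mid-year removes 0.5 / 62 = 0.8% of one arm's person-time, so the effect on GA days is small.

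**The case against.** The strongest reply is that the protocol already commits to keeping dropouts' data, that someone who leaves after month 6 still contributes baseline and 6-month forms, and that TAU is assessed on the same schedule as BA. That is right, and it limits the point to forms not completed after leaving or death. It does not settle it: an intention-to-treat statement cannot supply forms never filled in, and no method is named.

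Several stronger readings are tempting, and the documents do not support them.

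- **The record reviewers already identify self-harm.** GA covers admissions "due to psychiatric needs or following an act of self-harm or a suicide attempt, including possible following days with hospital admission". Because the criteria are alternatives, a psychiatric admission qualifies without anyone deciding whether self-harm or an attempt came first. Coding this would be new work. The record form (Bilaga 5a) is not in the documents, so its fields cannot be checked.
- **About a tenth of participants will die.** The Significance section says "These individuals are critically ill with mortality from suicide of approximately 10" per cent, but gives no time frame, so it cannot be applied to 12 months.
- **Suicides would materially flatter the GA result.** Days after death do add no GA days, but on the assumptions above the effect is small.
- **Attrition will differ strongly by arm.** The 15% and 35% in the illustration are assumed. With equal loss and equal dropout risk there is no false difference.
- **Question 5 promises suicide deaths.** It names self-harm and attempts, not completed suicide. The case for recording deaths rests on the population and on the need to account for everyone randomised.

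It is also fair that records may detect events differently by arm. This is why they can only supplement the questionnaires.

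**Conclusion.** The point holds in a limited form and is worth changing. As written, Question 5 has no data on participants after they leave or die, no method for the missing forms, and no record-based count of attempts or deaths. Classical mixed ANOVA, or ANCOVA of the later score on baseline, would drop incomplete cases unless values were imputed, despite the intention-to-treat statement.

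Bias between arms needs loss to be related to self-harm and to differ by arm. Neither can be established from the documents, so its size and direction are unknown. The 8-point example rests on assumed rates. The ±25-point contribution rests on 25% loss in each arm and marks only what the data could not rule out. Power is little affected (0.832 against 0.85, with ρ = 0.5 assumed).

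The documents also disagree on how self-harm is measured. Justification for Measures says "The clinician-administered self-harm measure is being validated in this study for use in clinical samples", whereas the measure descriptions and the Testing Schedule treat 5S-HM as a self-report, self-administered form. Either mode needs the participant, so the conclusion does not change, but the passages should be reconciled.

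**What to change.** 1. **Supplementary Question 5 outcome.** Add to the record extraction, for every randomised participant and subject to consent, the number of GA admissions and emergency visits following self-harm or a suicide attempt, plus date of death. Use the same 12 months from randomisation in both arms; the Testing Schedule dates baseline from randomisation in one arm and from the contract in the other. Apply one coding rule to both arms, with reviewers blind to arm where feasible. Report by arm whether or not questionnaires were completed.
2. **BA stays.** Leave them out of this comparison, because that contact exists in one arm only. List them separately.
3. **Questionnaires.** Analyse all available forms in a likelihood-based mixed model, and add a sensitivity analysis for non-random dropout, such as shifting the missing scores by arm until the conclusion changes.
4. **GA days.** Use days alive in follow-up as the exposure and report deaths separately. An exposure term does not itself count a death as an adverse result.
5. **Wording.** State whether records are still read after withdrawal, and reconcile the mode of administration of 5S-HM.

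The cost is some extra chart coding, a coding rule that separates attempts from other self-harm, and one more analysis. Records capture only hospital-treated events and may detect them differently by arm, so they complement the questionnaires and do not replace them.
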